Power Analysis for Aim 1. Assuming a range of within-person, across time correlations (0.1-0.7), with 144 participants (72 per arm), there will be 80% power, at the two-sided 0.05 significance level, to detect a difference between arms in slope of at least 0.030-0.052 SD units per month, or equivalently, 0.36-0.62 SD units over 12 months. If SDs of weight, BMI, and 6-MWT are similar to those observed previously (approximate weight SD 60, BMI SD 9, and 6-MWT SD 350) with the InSHAPE intervention and active control, these standardized effect sizes are equivalent to difference between arms of 21.6-36.0 lbs, 3.20-5.40 BMI units, and 6-MWT of 126-210m over 12 months. With attrition, power will be slightly lower, or equivalently, detectable differences slightly larger. To provide information on detectable differences if maximum attrition is experienced we also provide detectable differences assuming data from only 115 participants (80% of proposed sample size). In this case, the detectable difference increases to 0.034-0.059 SD units per month or 0.41-0.70 over 12 months yielding detectable weight of 24.6-42.0 lbs, BMI of 3.69-6.30, and 6-MWT of 143-245m over 12 months. True power/detectable difference likely lies in between for 144 vs. 115 participants. In the InSHAPE trial, 38% of participants in the active control arm and 51% of participants in InSHAPE achieved a clinically significant change in cardiovascular risk reduction. Because InSHAPE likely had a strong intervention effect with one-on-one personal fitness training and a gym membership for the active control, we estimate that percentages achieving clinically significant change in cardiovascular risk reduction in this study will be 20% for BEAT and 40% for PeerFIT. Assuming these proportions, there will be 86% power to detect a difference between arms in cardiovascular risk reduction, assuming measures of this outcome at 2 time points and within-person correlation of 0.5. With maximum attrition, the power is reduced to 77%.

Specific Aim 2 (Mechanism of Action): To test the mechanism hypotheses, parallel process latent growth curve models will be fit within a structural equation model (SEM) framework. These models allow for testing mediation of the treatment effect on weight and fitness by changes in self-efficacy (H2a) and peer social support (H2b). It is hypothesized that PeerFIT will have a greater effect on the change over time (slope) of

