We expect to enroll and randomize 144 participants in the Fit Forward Lifestyle Trial at study sites within the MA Department of Mental Health, Mental Health Center of Greater Manchester, Greater Nashua Mental Health Center at Community Council, and the Community Mental Health Affiliates. Given our stratified randomization procedure, the intervention allocation should be evenly divided between the experimental and control groups, at approximately 72 each. We chose this sample size because it is sufficient to detect weight loss that has public health significance. The proportion of participants who achieve clinically significant weight loss of $\geq 5\%$ and $\geq 10\%$ will be calculated because modest weight loss contributes to reduction in cardiovascular risk among overweight and obese individuals.

c. Define the target population:

This 12-month randomized controlled trial will recruit 144 young adults ages 18 to 35 with serious mental illness (SMI), defined by a chart DSM-V Axis I diagnosis of a qualifying SMI using diagnostic criteria as defined in the DSM-V for schizophrenia and psychotic disorders, mood disorders, anxiety disorders, and borderline personality disorder. Participants will be recruited from real-world settings providing services to clients within the Massachusetts Department of Mental Health community-based system of care, the Mental Health Center of Greater Manchester, the Greater Nashua Mental Health Center at Community Council, and the Community Mental Health Affiliates.

d. Vulnerable populations

Note: Certain populations are considered vulnerable to coercion and undue influence and are provided with additional protections when participating in a research study.

Identify any of the below populations which you plan to recruit for this study. In addition, complete the form(s) linked with each population as necessary and upload on the ‘Supporting Documents’ page in Rapport.

- [Pregnant Women, Fetuses and Neonates](#)
- [Children](#)
- [People with impaired decision-making capacity](#)

The following populations may also be considered vulnerable to coercion or other undue influence:

- Prisoners
- People who are economically disadvantaged
- The elderly
- People who are illiterate or do not speak English
- Students and employees

Describe any other potentially vulnerable population(s) and the additional protections provided to them:

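### Aim 1 power analysis, N=144: four of six converted detectable differences do not match the stated 0.36–0.62 SD, and the weight figures do not by themselves bear out section 9b

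*Combined protocol and SAP*

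**What the plan says.** The Power Analysis for Aim 1 (section 3.6.5) begins: "Assuming a range of within-person, across time correlations (0.1-0.7), with 144 participants (72 per arm), there will be 80% power", at two-sided 0.05. The detectable slope difference is 0.030–0.052 SD per month, restated as "0.36-0.62 SD units over 12 months". The SDs come from the earlier InSHAPE trial: "approximate weight SD 60, BMI SD 9, and 6-MWT SD 350". The conversion follows: "these standardized effect sizes are equivalent to difference between arms of 21.6-36.0 lbs, 3.20-5.40 BMI units, and 6-MWT of 126-210m over 12 months". For 115 participants (20% attrition) it gives 0.41–0.70 SD, or 24.6–42.0 lb, 3.69–6.30 BMI units and 143–245 m.

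For the H1b composite (at least 5% weight loss, or more than 50 m gained on the walk test) the plan notes that "38% of participants in the active control arm and 51% of participants in InSHAPE achieved a clinically significant change in cardiovascular risk reduction". It then assumes 20% for BEAT and 40% for PeerFIT, with 86% power, or 77% after attrition.

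Section 9b justifies the sample size thus: "We chose this sample size because it is sufficient to detect weight loss that has public health significance". Its next sentence turns to individual thresholds: "The proportion of participants who achieve clinically significant weight loss of" at least 5% and at least 10% will be calculated.

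**The concern.** The converted ranges are what a reader will use to judge whether a null or positive result on weight, BMI or walking distance is informative. Four of the six limits for the full sample do not follow from the standardised range in the same paragraph.

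Two further things look doubtful. Section 9b rests N on sensitivity to meaningful weight loss, yet the detectable weight differences are large against the 5% programme goal. And an SD of 60 lb with a within-person correlation as low as 0.1 implies very wide individual change over a year, which is hard to square with only 20% of BEAT meeting an either/or criterion that includes a 5% loss.

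**Working it through.** **Inputs.** From the plan: 72 per arm; visits at 0, 6 and 12 months; correlation ρ from 0.1 to 0.7; 80% power; two-sided 0.05; SDs 60, 9 and 350. The plan gives no unit for the 350; its own conversion treats it as metres. Not in the plan, and assumed below: mean baseline weight, mean change in BEAT, and normality of change.

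**Step 1. Reproduce the standardised figures.** Visit times have a sum of squares about their mean of 36 + 0 + 36 = 72 months². With n per arm, the detectable slope is 2.80 × √[2(1−ρ)/(n × 72)].
- n = 72, ρ = 0.7: 0.0301 SD/month.
- n = 72, ρ = 0.1: 0.0522 SD/month.

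This matches 0.030–0.052, so the SD-unit range is sound.

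**Step 2. Convert, N=144.**

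| Outcome | 0.36 × SD | 0.62 × SD | Printed |
|---|---|---|---|
| Weight (lb) | 21.6 | 37.2 | 21.6–36.0 |
| BMI | 3.24 | 5.58 | 3.20–5.40 |
| 6-MWT (m) | 126 | 217 | 126–210 |

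The printed upper limits are 36.0/60 = 5.40/9 = 210/350 = 0.60 SD. They are 3.2% too low (36.0/37.2 = 0.968); 3.20 is 1.2% too low. At ρ = 0.1, a 36.0 lb difference has 76.5% power rather than 80%.

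**Step 3. The neighbouring figures hold.** For 115: 0.41 × 60 = 24.6, 0.70 × 60 = 42.0, 0.41 × 9 = 3.69, 0.70 × 9 = 6.30, 0.41 × 350 = 143.5, 0.70 × 350 = 245. For H1b, with two time points at correlation 0.5 (variance factor (1 + 0.5)/2) and pooled variance, 20% against 40% gives 0.856 at 72 per arm and 0.771 at 57.5 per arm, matching 86% and 77%.

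**Step 4. Section 9b against the weight figures.** The most favourable value is 21.6 lb (ρ = 0.7, no attrition).
- As a 5% mean difference: 21.6/0.05 = 432 lb mean weight.
- As a 10% mean difference: 21.6/0.10 = 216 lb.

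For 10% of mean weight W at 80% power, the correlation needed is ρ = 1 − [0.10W/(12 × 60 × 2.80)]² × n × 72/2. With 144 participants that is about 0.70 at 216 lb and 0.57 at 260 lb; with 115, about 0.69 at 246 lb.

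**Step 5. Inputs against the 20% rate.** The SD of 12-month change is 60√[2(1−ρ)]: 80.5 lb at ρ = 0.1 and 46.5 lb at ρ = 0.7. With normal change and zero mean change, the share losing at least 5% is Φ(−0.05W/SD of change):
- 170 lb, ρ = 0.1: Φ(−8.5/80.5) = 0.458.
- 350 lb, ρ = 0.7: Φ(−17.5/46.5) = 0.353.

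That is about 35–46% on weight alone, against 20% planned for weight or walk. A 10 lb mean gain in BEAT lowers it to about 28–41%.

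**The case against.** The conversion slip is 1–3% on figures built from SDs that the plan itself calls approximate, and it alters no test, endpoint or sample size. That is fair as to size; the limits are still wrong.

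On section 9b, the strongest reply is that it never claims a 5% or 10% mean difference between arms. It speaks of weight loss of public health significance and then of individual proportions. That stands, and it is why Step 4 is only a benchmark. The plan does power one endpoint that contains individual 5% loss, but the 86% belongs to the weight-or-walk composite. No power is given for weight-loss proportions alone.

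On the input tension, the plan has a reason for setting BEAT below the earlier control's 38%: "Because InSHAPE likely had a strong intervention effect with one-on-one personal fitness training and a gym membership for the active control". That explains the direction but does not reconcile 20% with the SDs and correlations. More weighty is that the correlations are introduced as an assumed range, whereas the SDs and the 38% are reported as observed. If change was normal with zero mean, a 38% composite caps each component at 38%. Since Φ(−0.3055) = 0.38, the change SD is at most 0.05W/0.3055 for weight and 50/0.3055 for the walk. That gives ρ of at least about 0.88 at 180 lb, 0.75 at 260 lb, and 0.89 for the walk in metres. The assumed correlation range is therefore the likeliest source, and it errs on the conservative side. At ρ = 0.9 the detectable difference would be about 12.5 lb, which is 5% of 250 lb.

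**Conclusion.** The four limits (36.0 lb, 3.20 and 5.40 BMI units, 210 m) are wrong as written. This follows from the plan's own figures, taking SD 350 as metres as the plan does. The effect is to overstate sensitivity by about 3% at the upper limits and 1% at the lower BMI limit.

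The rest is conditional. The weight calculation does not support section 9b if that sentence is read as a 5% mean difference. Read as 10%, support depends on a mean weight that the documents do not give and on the correlation. The implied 35–46% weight response in BEAT sits poorly with 20%, given roughly normal change, little mean change and a mean weight of 170–350 lb.

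A reader might infer three stronger things, none of which the documents support:
- That the trial is underpowered for weight. The detectable differences depend on an assumed correlation that is probably too low.
- That the continuous inputs and the 20% rate strictly contradict each other. At ρ = 0.7, a mean gain in BEAT of about 22–31 lb (0.8416 × 46.5 − 0.05W, for 350 down to 170 lb) would bring the weight component to 20%. Such a gain is large, but the plan states no mean change.
- That a 10% difference is detectable only at ρ near 0.7 without attrition. Step 4 shows otherwise.

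**What to change.** Correct the N=144 limits to 37.2 lb, 3.24 and 5.58 BMI units, and 217 m, if 0.62 SD stands, and state the unit of the 6-MWT SD.

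Then restate the detectable weight and 6-MWT differences using the SD of 12-month change, or the within-person correlation, from the cited prior trial, and add a sentence on how those inputs sit with the 20% and 40% rates. Word section 9b to name the weight difference that the restated figures support, and say whether it means a mean difference or a responder proportion.

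The cost is editing two sections and one look-up in existing prior-trial data. N and data collection do not change. The corrected limits are slightly less favourable than those printed; the restated ones may move either way.

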Group Cohesion Scale: The Group Cohesion Scale-Revised (GCS-R) will be used to measure group cohesiveness within the PeerFIT group intervention. The GCS is a 25-item multidimensional scale rated 1=strongly disagree to 4 = strongly agree assessing domains such as interaction and communication, member retention, decision making, vulnerability among group members, and consistency between group and individual goals.¹⁴

Medial Outcomes Study Social Support Survey: The 19-item Social Support Survey will be used to assess four components of perceived availability of social support among participants in both conditions, including (1) Emotional support/Informational support, (2) Tangible support (including material support), (3) Positive social interaction (does person have friends that are available to have fun), and (4) Affectionate support (including loving and nurturing relationships). A total score and subscale scores are calculated. Higher scores indicate more social support.¹⁵

Participant Characteristics and Covariates

Demographic Characteristics: Demographic characteristics will be collected with a client demographics instrument (CDI) developed by our research group. Socio-demographic information will include age, sex,

gender, race/ethnicity, living situation, education, employment status, and other basic characteristics.

Psychiatric Diagnosis: Psychiatric diagnosis will be verified using the diagnosis in the chart at the agency providing mental health services.

Medication Use: Because medications can directly affect weight gain and level of physical activity, we will collect self-report data on the type of prescribed psychiatric medications (e.g., antidepressant, antipsychotic) and all other medications taken by participants at the time of assessment. We will ask participants to bring their current medications with them to the assessment appointment. The research interviewer will document all current prescription and non-prescription medications taken by participants. In addition, the research interviewer will review a list of psychiatric medications and FDA-approved and non-approved weight loss medication to assess whether participants are currently taking any of the medications on the list.

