self-efficacy than BEAT, and this change in self-efficacy will impact change in weight and fitness over time (slopes). PeerFIT is hypothesized to have a greater effect on peer social support slope than BEAT, and this change will also impact the change in outcomes. The product of coefficients (coefficient associated with path between treatment and mediator x coefficient associated with path between mediator and outcome) will be estimated along with bias-corrected bootstrap confidence intervals to determine the significance of the effect.

Power Analysis for Aim 2. The mechanism to be tested is the indirect effect of treatment on changes in weight and fitness (outcomes) through changes in self-efficacy and changes in peer social support (proposed mediators). The power for detection of the indirect effect depends on the size of each effect in the pathway.

The proposed parallel process growth curve analysis proposes mediation of the individual latent slopes, so power is computed at the individual-level although the individual-level latent slopes are estimated using data from observed mediators and outcomes measured at three time points (0, 6, and 12 months) improving precision. To compute power for detecting the mediated effect, we use results of a simulation study conducted by MacKinnon et al. In the simulation, indirect effects composed of effect of treatment on mediator and mediator on outcome were varied in size and significance was repeatedly tested via bias-correct bootstrap confidence intervals to obtain estimates of empirical power. This study showed that with 144 participants there will be approximately 80% power to detect a significant effect if the mediated effect is made up of two effects that are halfway between small and medium as defined by Cohen (explaining about 6.3% of the variance). For example, if treatment explains at least 6.3% of the variance in changes in self-efficacy, and changes in self-efficacy explain at least 6.3% of the variance in changes in weight, then there will be 80% power to detect this effect via bias-corrected bootstrap confidence intervals constructed around the indirect effect of treatment on changes in weight. If at least one of the effects (treatment to mediator or mediator to outcome) is larger (at least a medium effect explaining 13% of the variance), power is greater than 80%.

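### Aim 2 does not state joint entry of the two mediators, a direct arm path or baseline covariates, so a mediator with no effect on weight can be declared a mechanism

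*Combined protocol and SAP*

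**What the plan says.** - **Model (section 3.6.5, Specific Aim 2).** The plan states that "parallel process latent growth curve models will be fit within a structural equation model (SEM) framework". Self-efficacy and peer support carry separate labels, H2a and H2b, and are described one after the other.
- **Test.** The effect is the product of two coefficients ("coefficient associated with path between treatment and mediator x coefficient associated with path between mediator and outcome"), with "bias-corrected bootstrap confidence intervals to determine the significance of the effect".
- **Power Analysis for Aim 2.** The plan states that "with 144 participants there will be approximately 80% power to detect a significant effect" when each of the two paths explains about 6.3% of variance. The worked example is a single chain from arm through self-efficacy to weight.
- **Covariates (section 3.6.2, Participant Characteristics and Covariates).** On medication the plan says: "Because medications can directly affect weight gain and level of physical activity, we will collect self-report data". Table 1 schedules the medication list and CES-D at 0, 6 and 12 months.
- **Support measures (Table 1).** The Social Provisions Scale (SPS) is collected in PeerFIT only, and the MOS Social Support Survey in both arms.

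No section states that both mediators are in one outcome equation, that a direct arm path is included, or which covariates enter the mediator-to-outcome path. None states the no-confounding assumption on which that path depends.

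**The concern.** Random assignment makes the arm-to-mediator path a causal contrast. It does nothing for the mediator-to-outcome path, because nobody is randomised to gain confidence or support. Two things can load onto that second coefficient.

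The first is the other mediator. One arm is meant to raise both, through overlapping components, so their changes are likely to be correlated. If one of them works and is left out of the equation, part of its effect is credited to the other.

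The second is a common cause. Low mood or a weight-affecting drug may influence both confidence to exercise and weight. The plan itself says that medication affects weight and activity. The eligibility criteria allow discontinuation and dose changes of olanzapine and clozapine, and do not exclude weight-loss medication.

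At stake is whether Aim 2 could name self-efficacy or peer support as a mechanism when it has no effect on the outcome.

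**Working it through.** **Inputs from the plan.** N = 144, allocated 1:1; each path explains 6.3% of variance; bias-corrected bootstrap. No confidence level is given for Aim 2, so 95% is assumed, matching Aim 1 ("at the two-sided 0.05 significance level"). As in the plan's own power paragraph, slopes are treated as individual-level variables.

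**Set-up.** Standardised coefficient = √(R²/(1−R²)) = √(0.063/0.937) = 0.259. The arm-to-mediator coefficient a comes from regressing M on arm. The mediator-to-outcome coefficient b comes from regressing Y on arm and M. The interval for a×b uses 1,000 resamples. Runs had 1,000 to 2,000 simulated trials per setting.

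**Step 1: the plan's figure.** Simulated power is 80.4% with the direct arm path and 82.0% without it, against the stated figure of about 80%. With one path at 13%, power is 88-93%, in line with the plan's statement that it exceeds 80%. The power figure reproduces, so the issue is model specification. At N = 115 (the Aim 1 attrition case) power is about 70%; the plan gives no Aim 2 figure for attrition.

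**Step 2: the other mediator omitted.** Let the omitted mediator work (b₁ = 0.259), let the tested one be inert, and let their residual correlation be ρ. The inert mediator's coefficient then tends to ρ×b₁, and its product to a×ρ×b₁ = 0.259² × ρ = 0.0672ρ. That is 0.020 at ρ = 0.3 and 0.034 at ρ = 0.5; the simulated means were 0.019 and 0.033. The inert mediator is credited with a fraction ρ of a real indirect effect.

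Chance of declaring the inert mediator, N = 144:

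| ρ | Other mediator omitted | Other mediator included |
|---|---|---|
| 0 | 8% | 7% |
| 0.1 | 10% | not run |
| 0.2 | 12.5% | not run |
| 0.3 | 17-20% | 8% |
| 0.5 | 36-37% | 7-8% |
| 0.7 | 59% | 7% |

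Ranges span separate runs. At N = 115 the omitted-mediator rates are 8%, 15%, 29% and 45% at ρ = 0, 0.3, 0.5 and 0.7. The floor of about 8% is the usual slight excess of the bias-corrected bootstrap over 5%.

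**Step 3: a common cause omitted.** If a cause correlates r with both the mediator slope and the outcome slope, an inert mediator's coefficient tends to r² and its product to 0.259×r². At r = 0.3 this is 0.259 × 0.09 = 0.023, and at r = 0.4 it is 0.259 × 0.16 = 0.041; the simulated means were 0.023 and 0.042. The false-positive rate is about 7% at r = 0.1, 11-12% at 0.2, 22-24% at 0.3 and 51-52% at 0.4. With the cause in the model it is 6-9%.

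**Step 4: direct arm path omitted.** An arm effect on the outcome of 6.3% that bypasses the mediator gives 14% by itself, against 7% with the path included.

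**Step 5: what joint entry costs.** Power for a real 6.3%/6.3% effect, adjusting for a correlated but inert second mediator at N = 144, is 82% at ρ = 0, 80% at 0.3, 75% at 0.5 and 60% at 0.7.

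**The case against.** A reader might infer that the plan commits to separate one-mediator models. It does not. Section 2 states H2 as one hypothesis with both mediators, the Aim 2 power paragraph describes an indirect effect through both, and a structural equation model can hold both. The separate labels and the single-chain example lean the other way. The text is silent on joint entry and does not exclude it.

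A reader might also infer that medication and CES-D are collected and then ignored. They sit under a heading that calls them covariates, and the Evaluation of Randomization paragraph compares the arms on key covariates. What is missing is their assignment to the Aim 2 model.

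The size of the problem is open to challenge. The documents give no correlations, and at 0.1-0.2 the excess over the 8% floor is small. A common cause of 0.3-0.4 explains 9-16% of variance in both slopes (0.3² and 0.4²), more than the 6.3% the plan assumes for its own paths, and nothing in the documents shows that baseline mood or medication is that strong. Even at ρ = 0.5, about 63% of trials would not declare the inert mediator. It would therefore be wrong to say that whichever mediator works will make the other look like a mechanism; it can.

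These points limit the strength of the claim. They do not supply the missing specification, and the choice left open can change the conclusion.

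**Conclusion.** The concern holds as a gap in specification with a demonstrable consequence. The Aim 2 test is described only as a product of two coefficients. Joint entry, a direct arm path and baseline adjustment are all unstated for a path that randomisation does not protect. Under the plan's own N and path sizes, the chance of declaring an inert mediator runs from about 8% to 36-37% as residual mediator correlation goes from 0 to 0.5, and from about 7% to 51-52% as an omitted common cause goes from 0.1 to 0.4.

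These rates rest on assumed correlations, a 95% interval and slopes treated as observed. Error in slopes estimated from three visits would change the exact rates and may leave some bias after adjustment.

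The stated 80% power is not in error, and the Aim 1 effectiveness conclusions are untouched.

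**What to change.** State in the SAP, before analysis:

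1. For each outcome, one parallel process model containing both mediator slopes and a direct path from arm to outcome slope.
2. Mediator and outcome slopes regressed on their own latent intercepts. Baseline values should not be added as separate covariates, since time 0 already informs the intercept.
3. The same slopes regressed on a short pre-specified baseline set: CES-D, antipsychotic or weight-loss medication use, age and sex.
4. Each specific indirect effect tested in that model and reported as conditional on no unmeasured mediator-outcome confounding, which adjustment for measured causes cannot remove.
5. A support measure available in both arms. The Aim 2 text compares peer support between arms while Table 1 collects SPS in PeerFIT only, so these must be reconciled. MOS is collected in both arms but measures general rather than peer-group support, so using it changes what H2b tests.

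**Cost.** No new data are needed. Power falls below the stated 80% once the mediators correlate at about 0.5 (75%) and substantially at 0.7 (60%). The model also grows: counting medication use as one indicator, four covariates on three slopes add 12 paths, plus three slope-on-intercept paths. Information is limited to three visits and perhaps 115 completers, and the note under Table 1 drops physical measures from 12-month assessments held under the distancing restrictions. The covariate set should therefore stay short.

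### Aim 2's 80% power is a figure for slopes free of estimation error; the plan makes no allowance for estimating them from three visits, and the remark about precision does not support it

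*Combined protocol and SAP*

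**What the plan says.** Section 3.6.5 (Analyses for Study Aims and Hypotheses) plans parallel process latent growth curve models for Aim 2. The indirect effect is tested as a product of coefficients with a bias-corrected bootstrap interval.

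The paragraph headed Power Analysis for Aim 2 says that the analysis "proposes mediation of the individual latent slopes, so power is computed at the individual-level", and then that the "latent slopes are estimated using data from observed mediators and outcomes measured at three time points (0, 6, and 12 months) improving precision".

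The power figure itself is taken from a published simulation study, in which "indirect effects composed of effect of treatment on mediator and mediator on outcome were varied in size". The plan concludes: "This study showed that with 144 participants there will be approximately 80% power to detect a significant effect", provided that each of the two paths explains about 6.3% of variance. Its worked example applies this to variance in changes in self-efficacy and in weight and repeats the claim: "then there will be 80% power to detect this effect via bias-corrected bootstrap confidence intervals". Nothing in the paragraph mentions error in the slopes, a slope reliability or a residual variance, and the example does not say whether the changes are latent or observed.

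**The concern.** The planned model relates latent slopes, and each person's slope must be inferred from single assessments at 0, 6 and 12 months. A growth model corrects the path between slopes for attenuation, but it pays for this with larger standard errors. Compared with slopes known exactly, at the same latent effect sizes, power can only fall. If the 80% already assumes exact slopes, it leaves nothing for this cost, and a remark that repeated visits improve precision points the reader the wrong way.

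Mediation is one of the trial's two specific aims. If the test is weaker than stated, a null result could be given more weight against the proposed mechanisms than it deserves. The issue arises even if all 144 participants are retained, so it is separate from attrition.

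**Working it through.** **Inputs.** From the plan: N = 144, randomized 1:1; 6.3% of variance per path; bias-corrected bootstrap test; visits at 0, 6 and 12 months. Assumptions: 95% two-sided interval (the two-sided 0.05 level is stated for Aim 1 only), no direct effect, residual slope variances of 1, and a slope reliability ρ, meaning the share of within-arm variance in estimated slopes that is true variance. The documents give no value for ρ.

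**Effect size.** A coefficient of 0.26 gives 0.26²/(1 + 0.26²) = 0.0676/1.0676 = 6.3%. The plan's larger case of 13% matches 0.39: 0.1521/1.1521 = 13.2%.

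**Reproducing the plan's figure.** I simulated a single-mediator model with error-free slopes, a = b = 0.26, and a bias-corrected bootstrap with 1,000 resamples. In 5,000 trials, power was 81.1% with a normal treatment variable and 81.6% with a 72/72 binary one (Monte Carlo SE 0.6 points). Shorter runs gave 82.5% and 82.9%. The stated 80% therefore corresponds to slopes without error.

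**What the 6-month visit adds.** In 12-month units the centred times are −0.5, 0 and 0.5, with sum of squares 0.25 + 0 + 0.25 = 0.5. The least-squares slope weights are therefore −1, 0 and +1. Visits at 0 and 12 months alone give the same sum of squares and weights −1 and +1. With independent errors of equal variance, the middle visit adds nothing to an individual's linear slope. It helps only to separate error variance from true slope variance.

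**Adding slope error, 6.3% per path on the latent slopes, all 144 retained.** The bootstrap ranges span separate runs; a run of 1,000 trials has a Monte Carlo SE of up to 1.6 points. The last column is a cross-check from the expected information of the three-visit growth model, as the chance that both paths are significant.

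| Slope reliability (mediator / outcome) | Bias-corrected bootstrap on estimated slopes | Growth model, both paths significant |
|---|---|---|
| about 1.0 | 81–83% | 77% |
| 0.95 / 0.95 | 74–78% | 72% |
| 0.9 / 0.9 | 72–75% | 67% |
| 0.8 / 0.8 | 62–64% | 55% |
| 0.7 / 0.7 | 50–54% | 42% |
| 0.5 / 0.5 | 24–27% | 19% |
| 0.9 / 0.95 | 76% | – |
| 0.7 / 0.95 | 58–64% | – |

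The last column starts from 77% because it is a different test, so its losses must be read from 77%. Its arithmetic is as follows:
- SE(a) = 1/√(144ρ), which is 0.083 at ρ = 1, 0.088 at 0.9 and 0.100 at 0.7.
- SE(b), from the information matrix, is 0.083, 0.093 and 0.123 at the same values.
- Power per path is Φ(0.26/SE − 1.96). At 0.9 this gives 0.841 × 0.796 = 0.67; at 0.7 it gives 0.742 × 0.565 = 0.42.

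**If 6.3% means observed change.** Power stays at about 81%, but the latent effects must be larger. At reliability 0.7 for both variables, the treatment path needs about 0.063/0.7 = 9% of latent variance, and the mediator-to-outcome path about 0.063/(0.7 × 0.7) = 13%. The second is what the plan itself calls a medium effect.

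**Where reliability might lie (illustration only).** If a share e of total variance is error and r is the correlation across visits, the reliability of 12-month change is 1 − e/(1 − r). The Aim 1 power paragraph uses r = 0.1–0.7. Borrowing that range, e = 0.10 gives 1 − 0.10/0.9 = 0.89 down to 1 − 0.10/0.3 = 0.67, and e = 0.05 gives 0.94 down to 0.83.

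**The case against.** A reader might infer that Aim 2's true power is well below 80%. The documents do not support that as an unconditional statement. It needs a low slope reliability, which they do not give, and it needs 6.3% to be a share of latent-slope variance, which the worked example leaves open. On the observed-change reading about 81% stands, and at reliability 0.95 the loss is only a few points. Both objections hold, and they limit the conclusion.

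Nor is this an arithmetic error, since the 80% reproduces. The plan openly says that the slopes are estimated, and it does not claim more power than the simulation gave. That the published simulation used error-free variables is an inference from the reproduction and from the plan's description, which mentions only path sizes.

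Low reliability is also hard to believe for the weight readings themselves. With the plan's SD of 60 lb, 10% error variance would be an error SD of 60 × √0.10 ≈ 19 lb, whereas section 3.6.2 specifies a calibrated scale and duplicate readings. However, departures of a person's course from a straight line also count as error in a linear growth model, and the intervention moves from an intensive to a lower-intensity phase at 6 months. A precise outcome does not remove the problem either. Exercise self-efficacy is a five-item self-report scale, and with mediator reliability 0.7 and outcome 0.95 power is still about 58–64%.

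Finally, neither calculation above is the planned latent model with the planned bootstrap, so the figures are indicative.

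**Conclusion.** The point holds in a conditional form. The plan names latent slopes as its target and quotes a power that corresponds to slopes free of estimation error. It budgets nothing for estimating them, and its precision remark gives no support for the 80%. For latent effects of 6.3% per path, 80% is in effect an upper limit.

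The size of the shortfall cannot be fixed from the documents. It is a few points if reliability is about 0.95, and becomes large at 0.8 or below, where power is 62–64% or less. If 6.3% was meant as observed change, the power stands but the latent effects it requires are understated. These conclusions assume linear change, independent equal-variance errors and no attrition. The trial's sample size is unaffected, because section 9b justifies it by weight loss and not by mediation.

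**What to change.** In Power Analysis for Aim 2:

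- Delete the closing words of the sentence on latent slopes that claim a gain in precision.
- State whether 6.3% is a share of latent or of observed change variance.
- If latent, state that 80% is an upper limit, reached only if slopes are estimated essentially without error. If observed, state the larger latent effects implied, for example about 9% and 13% at reliability 0.7.
- Restate power from a simulation of the planned three-visit parallel-process model with the planned bias-corrected bootstrap, over a stated range of slope reliability that may differ between mediator and outcome.

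The cost is a few hours of simulation and a less favourable stated figure. Participants and visits do not change.
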